Blood Draws, Pain Testing & Drug Protocol. Figure 3 depicts the timing of blood draws, heat capsaicin procedures, quantitative sensory testing, and drug administration. This protocol will be implemented in the mornings after the US night and the second FA night (FA2). Drs. [name] and [name] have experience conducting all of the pain testing procedures(90-93). Drs. [name], [name], and [name] have extensive expertise studying the effects of opioid agonists(94, 95). All pain testers complete a rigorous training process that includes inter-rater reliability testing ($\kappa > .80$). Participants are permitted to terminate any of the procedures at any time. The following procedures will be conducted in an identical fashion on both visits. All assessments will be conducted by BSMP staff, who will be blind to subject conditions.

Blood Draws & Handling Procedures. Subjects will remain in a semi recumbent position during the procedure. Approximately 30 minutes after Lights On (i.e., wake), the nurse will insert a single port lumen peripheral catheter in an upper extremity vein, contralateral to the arm used for capsaicin testing. A continuous saline infusion at 250cc/h will be maintained. The line will be flushed with saline before and after all blood draws, and will remain installed until the final QST procedure is complete. As shown in Figure 7, seven blood draws will be obtained (3 pre-injection and 4 post-injection). Blood draws 1 and 2 will be obtained approximately 60 minutes apart, prior to the 35 minute heat capsaicin procedure, to provide a resting baseline. After the initial capsaicin procedure, all blood will be drawn prior to each rekindling. Blood will be immediately transported to the Rheumatology Disease Research Core for immediate preparation by the RDRC tech.

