Heat-Capsaicin and Rekindling Procedures. We will utilize procedures similar to established protocols(96, 97). Heat will be delivered using a computer driven peltier heating element (Medoc TSA II). The procedure involves a 35 minute sensitization period. A 10.24 cm² treatment site, the size and shape of the thermode will be randomly assigned and marked on either a lower or upper, non overlapping surface of the ventral forearm opposite the arm from which blood is drawn. Lower and upper treatment sites will be counterbalanced across admissions. The thermode is secured on the skin with velcro straps and heated at 45°C for 5 minutes. Pain ratings will be collected once every minute on a 0-100 VAS (“no pain”, “most extreme pain imaginable”). An open square, raised adhesive frame patch (internal dimensions same as thermode) is immediately applied to the borders of the treatment site and Capsaicin cream (0.1% Capsaicin)(90) is evenly spread onto the skin and permitted to absorb for 30 minutes. This induces moderate (Mean = 48.25± 27.93), but well tolerated pain. The raised frame prevents spillage or leakage of capsaicin outside the treatment site. Capsaicin is removed, blood draw 3 is obtained, and QST1 is performed as described below. Following morphine/placebo injection and the subsequent 40 minute rest, the treated skin will be rekindled a total of four times at 40 min intervals by heating the treatment site with the thermode at 40°C for 5 min. Following each rekindling episode, a series of QST procedures to quantify 1^o and 2^o Hyperalgesia will be conducted. Studies have demonstrated excellent test-retest stability in hyperalgesia measurements over 4 rekindlings(96, 97, 97). The timing associated with these procedures may vary as a function of experimental demands.

Quantitative Sensory Testing (QST) Procedures. All tests will be conducted in the order described.

Primary Hyperalgesia. Heat-Pain Threshold(HPT_h) will be assessed using an ascending method of limits paradigm prior to application of heat capsaicin, after the 35 minute sensitization period and after each rekindling. The thermode is secured to the treatment site and the temperature gradually increased (rate of rise = .5°C/sec) from a pre-set baseline (31°C), until the subject indicates when

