Hypothesis 3.a. (Sleep disruption increases activation of markers of inflammation): We will first compute area-under-the-curve-ground (AUC-G) and -increase (AUC-I) values following standard formulas(134) for the inflammatory markers. AUC allows us to simplify the analysis of the repeated measures data to increase power(134). AUC-G represents the total amount of inflammation during the pre-drug administration segment (blood draws 1-4), whereas AUC-I represents the level of increase in inflammation in response to heat capsaicin (blood draws 3-4), relative to the within-condition baseline levels (blood draws 1 & 2). Mixed effect models will test the difference in marker AUCs between sleep conditions.

Hypothesis 3.b. (Markers of inflammation mediate the effects of sleep disruption on: 1) HA and 2) diminished opioid analgesia): Following the MacArthur approach(135) we will first establish relationships between the markers and both hyperalgesia (HA) and sleep disruption (SD). Thus, these analyses will only be conducted if tests of Hypothesis 3.a. indicate a relationship between SD and activity of a specific marker. For these markers, we will then test the relationship between marker activity and HA using mixed effects models. When significant, interactions between SD and marker activity will be taken as evidence of *mediation* rather than *moderation*, as should a main effect of marker activity after controlling for this interaction and the main effects of SD(135). These analyses use only data from the pre-drug administration segment ;therefore, the placebo and opioid groups are combined. Mixed effects models will test the relationship between marker activity and diminished opioid analgesia, allowing for correlation within individuals across sleep conditions and pre- and post-drug segments. Statistical significance of the main effect of marker activity, the interaction between drug condition and marker activity, or the interaction between drug, marker, and SD will be taken as evidence of a mediating effect of marker activity.

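### The inflammatory AUCs labelled pre-drug include blood draw 4, which is taken after the morphine or placebo injection and after QST1, the outcome it is meant to explain

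*Combined protocol and SAP*

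**What the plan says.** Section 7.b, Hypothesis 3.a, defines two summaries for each inflammatory marker. For the first, "AUC-G represents the total amount of inflammation during the pre-drug administration segment (blood draws 1-4"). For the second, "AUC-I represents the level of increase in inflammation in response to heat capsaicin (blood draws 3-4"), measured against draws 1 and 2. Mixed models then compare these AUCs between sleep conditions; no drug term is mentioned.

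Hypothesis 3.b takes forward only markers for which Hypothesis 3.a shows an effect of sleep disruption. For the hyperalgesia part it says "These analyses use only data from the pre-drug administration segment", and gives this as the reason for combining the morphine and placebo groups.

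The sampling schedule is in Section 4.a. Under Blood Draws & Handling Procedures, "seven blood draws will be obtained (3 pre-injection and 4 post-injection"). The same paragraph says "Blood draws 1 and 2 will be obtained approximately 60 minutes apart, prior to the 35 minute heat capsaicin procedure, to provide a resting baseline", and then "After the initial capsaicin procedure, all blood will be drawn prior to each rekindling". Under Heat-Capsaicin and Rekindling Procedures, "Capsaicin is removed, blood draw 3 is obtained, and QST1 is performed as described below", and later "Following morphine/placebo injection and the subsequent 40 minute rest, the treated skin will be rekindled a total of four times". The Design paragraph puts the injection after QST1 and counts one pre-drug and four post-drug QST sessions.

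**The concern.** The analysis section counts four pre-drug draws and the procedures count three. If the analysis section is followed literally, there are four consequences.

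- **Pooling.** The two drug groups are combined because the data are said to be pre-drug. With draw 4 included, everyone randomised to morphine (two of the four sequences) contributes a sample taken under morphine.
- **Temporal order.** QST1 is the only post-capsaicin hyperalgesia measurement made before the drug. Draw 4 follows it in both arms, so part of the mediator comes after the outcome, whatever morphine does to cytokines.
- **Meaning of AUC-I.** Between draws 3 and 4 participants undergo QST1, which includes immersion of the hand in 4°C water for up to 5 minutes, and then the injection. The change over that interval is not a response to heat-capsaicin alone.
- **Gating.** Hypothesis 3.a decides which markers reach the mediation tests, so an error in its AUCs carries forward.

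Several of these markers are primary outcomes for Aim 3 (Table 2).

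**Working it through.** **Step 1: order of events, from Section 4.a.**

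| Event | Source | Relative to injection |
|---|---|---|
| Draw 1 | Blood Draws | before |
| Draw 2, about 60 min later | Blood Draws | before |
| Heat-capsaicin, 35 min | Heat-Capsaicin | before |
| Draw 3, after capsaicin is removed | Heat-Capsaicin | before |
| QST1 | Heat-Capsaicin; Design | before |
| Injection | Design | – |
| 40-min rest | Design; Heat-Capsaicin | after |
| Draw 4, before rekindling 1 | Blood Draws | after |
| Draws 5–7, before rekindlings 2–4 | Blood Draws | after |

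This gives 3 draws before and 4 after, which reproduces the split in the Blood Draws paragraph. It does not reproduce the four pre-drug draws of Hypothesis 3.a. This step needs no assumption.

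**Step 2: how much draw 4 counts in AUC-G.** Two inputs are missing, so I assume them: draw 2 is taken immediately before capsaicin, and QST1 lasts q minutes. I also take draw 4 at the end of the 40-minute rest. The draws then fall at 0, 60, 60 + 35 = 95, and 95 + q + 40 = 135 + q minutes.

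- Window: T = 135 + q
- Share of the window after injection: 40 / T
- Trapezoid weight of draw 4: (40 + q) / (2T)
- Share of the window between draws 3 and 4: (40 + q) / T

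| q (min) | T (min) | After injection | Weight of draw 4 | Draw 3–4 segment |
|---|---|---|---|---|
| 0 | 135 | 29.6% | 14.8% | 29.6% |
| 15 | 150 | 26.7% | 18.3% | 36.7% |
| 20 | 155 | 25.8% | 19.4% | 38.7% |
| 30 | 165 | 24.2% | 21.2% | 42.4% |
| 40 | 175 | 22.9% | 22.9% | 45.7% |

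In AUC-I, draw 4 is one of two response samples.

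**Step 3: sensitivity to when draw 4 is taken.** The text says only that it precedes the rekindling. If it came t minutes after injection, the post-injection share would be t / (95 + q + t) and the weight (q + t) / [2(95 + q + t)]. At t = 20:

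- q = 15: share 20/130 = 15.4%, weight 35/260 = 13.5%
- q = 30: share 20/145 = 13.8%, weight 50/290 = 17.2%

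The shares fall, but the sample is still post-drug and after QST1.

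**Step 4: what reaches the Hypothesis 3.a contrast.** Let m_FA and m_US be morphine's effect on the marker at draw 4 after forced awakenings and after uninterrupted sleep, p the proportion on morphine, and w the weight of draw 4. With AUC-G expressed as a time average, the pooled sleep contrast is shifted by p × w × (m_FA − m_US). With equal allocation (p = 0.5, assumed) and w = 0.183 to 0.212, the shift is 0.092 to 0.106 times that difference. It is zero if morphine acts equally under both sleep conditions. The documents give no value for m_FA or m_US, so the shift cannot be turned into a bias.

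**The case against.** The strongest reply is that this is a numbering slip. The plan states twice that the segment is pre-drug, and an analyst who combined that intention with the three-draw count would leave out draw 4. That is possible, but the slip would have to occur twice in one sentence, because AUC-I also names draw 4. Correcting it changes both definitions, and no other text says which reading applies.

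The consequences are also narrower than they may first appear. Drug is a between-subject factor, the same at both admissions, so a morphine effect equal across sleep conditions cancels in Hypothesis 3.a. In the pooled hyperalgesia analysis, morphine is randomised and given after QST1, so its effect on draw 4 should mainly add noise and weaken associations, not create false mediation. Both points stand. Neither restores the temporal order, nor makes the reason for pooling true. Equality across sleep conditions is also not a safe premise here, since Aim 2 hypothesises that sleep disruption alters morphine's effect on pain.

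Three smaller points stand. The 40-minute timing of draw 4 is an upper limit for a sample taken before the rekindling, and the protocol allows timings to vary. Trapezoid weights measure influence, not bias. Hypothesis 3.b speaks of marker activity without naming an AUC, so the link between the AUCs of 3.a and the mediator of 3.b is inferred, although no other marker summary is defined.

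**Conclusion.** The concern holds. The analysis section treats draw 4 as pre-drug; the procedures make it post-drug and place it after QST1. That finding rests on the text alone. Under the assumed timings (draw 2 just before capsaicin, QST1 of 15 to 30 minutes, draw 4 at 40 minutes), about a quarter of the AUC-G window lies after injection and draw 4 carries roughly a fifth of the weight. Allowing QST1 to last 0 to 40 minutes widens these to 23–30% and 15–23%.

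The size of any bias is unknown. For Hypothesis 3.a it depends on a drug-by-sleep effect on the markers. For the hyperalgesia part of Hypothesis 3.b, the broken temporal order and the false basis for pooling apply regardless. Aims 1 and 2 do not use these AUCs. Because the definitions govern primary Aim 3 outcomes, they must be corrected before any AUC is computed; choosing the draws after seeing the data would be a post hoc decision.

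**What to change.** In Section 7.b:

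- Define pre-drug AUC-G on draws 1 to 3 (about 95 minutes under the timings above).
- Define the capsaicin response as draw 3 relative to the baseline from draws 1 and 2.
- Use only these summaries in Hypothesis 3.a and in the pooled hyperalgesia analysis of Hypothesis 3.b, and name them there as the marker activity.
- If draws 4 to 7 are used, put them in a separate post-drug analysis with drug and drug-by-sleep terms.

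This changes wording only: the sampling schedule, visits and sample size stay as they are. The cost is that the capsaicin response becomes a single-sample change score, taken just after the 35-minute procedure, and is no longer an area over two samples. It may be noisier and would miss a later rise. The documents give no data from which to size that loss.

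### For hyperalgesia in Hypothesis 3.b, the marker summaries carried forward include blood drawn after capsaicin has induced the hyperalgesia, so the rule cannot tell mediation from reverse causation

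*Combined protocol and SAP*

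**What the plan says.** Section 7.b, Hypothesis 3.a, defines two summaries per marker. "AUC-G represents the total amount of inflammation during the pre-drug administration segment (blood draws 1-4"), and "AUC-I represents the level of increase in inflammation in response to heat capsaicin" (draws 3-4), taken relative to the baseline from draws 1 and 2. Mixed models compare these AUCs between sleep conditions.

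Hypothesis 3.b takes forward only markers that show a sleep effect in 3.a and relates what it calls marker activity to HA. A significant sleep-by-marker interaction, or a marker main effect after adjustment, counts as mediation. The HA analyses are limited to the pre-drug segment, and the drug groups are combined for that reason.

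The timing is in section 4.a:
- Blood Draws & Handling Procedures: "Blood draws 1 and 2 will be obtained approximately 60 minutes apart, prior to the 35 minute heat capsaicin procedure".
- Heat-Capsaicin and Rekindling Procedures: "Capsaicin is removed, blood draw 3 is obtained, and QST1 is performed as described below".
- Design paragraph: the injection is given once QST1 is complete. There is one pre-drug QST session and four post-drug sessions.
- Blood Draws & Handling Procedures: "seven blood draws will be obtained (3 pre-injection and 4 post-injection"), and "After the initial capsaicin procedure, all blood will be drawn prior to each rekindling".

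**The concern.** Mediation of HA by inflammation is a directional claim: sleep disruption raises the marker, and the marker raises HA. The HA read at QST1 is produced during the heat-capsaicin period. A marker level taken at the end of that period may itself respond to the pain or to the stimulus. AUC-I isolates that response by subtracting the resting level; AUC-G dilutes it with two resting draws. The 3.a precondition does not remove the ambiguity, because a chain from sleep to HA to marker also produces a sleep-marker association.

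Draw 4 adds a second problem. If it follows the injection, a sample that morphine could affect enters an analysis that pools the arms on the ground that it is pre-drug.

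At stake is what a positive HA result in 3.b may be called. The plan contains no mediator restricted to draws 1-2, no test of the reverse path and no sensitivity analysis for time order.

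**Working it through.** **Order of events on a test day, from section 4.a**

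| Event | Relative to induced HA | Relative to QST1 | Relative to injection |
|---|---|---|---|
| Draws 1, 2 | before | before | before |
| Heat-capsaicin, 35 min | induces it | before | before |
| Draw 3 | after | before | before |
| QST1 | after | – | before |
| Injection | after | after | – |
| Draw 4 (first of the 4 post-injection draws, before the first rekindling) | after | after | after |

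With 3 draws before injection and 4 after, draw 4 cannot be pre-drug. Section 7.b nevertheless puts draws 1-4 in the pre-drug segment.

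**The plan's own figure.** The only stated number touching this test is Aim 3 power: 80% at N=80, effect 0.56, alpha 0.01. Treating the two conditions as independent means, 0.56/√(2/80) = 3.54 and 3.54 − 2.576 = 0.97, so power is about 83%. Within-person correlation would raise it. The plan does not give the correlations used in its simulation, so the 80% can be neither reproduced nor faulted. The point does not depend on it.

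**Size under pure reverse causation.** Inputs from section 7.b: N=80, alpha 0.01 (taken as two-sided), sleep effect on HA 0.40 (Aim 1), sleep effect on resting markers 0.56 (Aim 3). Assumed, because the documents give no value:
- no effect of the marker on HA;
- HA raises draw 3 by c = 0.2, 0.3 or 0.5 SD per SD;
- HA correlation across sleep conditions 0.5;
- half of the stable marker variance shared across conditions;
- draw-to-draw correlation ρ = 0.5, 0.7 or 0.85;
- about 40 minutes between draws 2 and 3, giving trapezoid weights 0.3/0.5/0.2 for AUC-G.

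Draw 4 is left out because its status is in conflict. Tests are on FA-minus-US changes, and AUC-I is draw 3 minus the mean of draws 1-2.

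The AUC-I change has mean 0.40c and variance c² + 3(1 − ρ). For c=0.5, ρ=0.85 the mean is 0.20 and the SD is √(0.25+0.45) = 0.837. The precondition statistic is then centred at 0.20/0.837 × √80 = 2.14 against a critical value of 2.64, so it is met in about 31% of trials. The AUC-I–HA correlation is 0.5/0.837 = 0.60, so the link is nearly always found.

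Simulation, 4000 trials per row, % of trials. Joint means precondition and link both p<0.01:

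| ρ | c | AUC-I precondition | AUC-I link | AUC-I joint | AUC-G joint | Draws 1-2 joint |
|---|---|---|---|---|---|---|
| 0.5 | 0.2 | 2.9 | 12.9 | 0.2 | 1.6 | 1.1 |
| 0.5 | 0.3 | 4.2 | 32.0 | 1.2 | 1.9 | 1.0 |
| 0.5 | 0.5 | 10.0 | 83.3 | 8.0 | 5.0 | 0.8 |
| 0.7 | 0.2 | 3.4 | 23.1 | 0.6 | 1.5 | 0.9 |
| 0.7 | 0.3 | 6.4 | 55.9 | 3.3 | 2.2 | 0.8 |
| 0.7 | 0.5 | 16.7 | 96.8 | 16.0 | 3.9 | 0.9 |
| 0.85 | 0.2 | 6.1 | 50.7 | 2.7 | 1.6 | 1.0 |
| 0.85 | 0.3 | 12.2 | 90.2 | 10.8 | 2.2 | 1.2 |
| 0.85 | 0.5 | 30.9 | 100 | 30.9 | 5.0 | 1.1 |

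At c=0 the AUC-I joint rate is at most 0.1%, and the other two sit at the nominal 1%. At ρ=0.9 and c=0.5 the AUC-I joint rate reaches 42%. If AUC-I is formed from draw 1 as baseline, its joint rate stays under 2% throughout, because draw 3 then carries a weight of only 0.2.

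**A second set-up.** Here the resting marker is unrelated to sleep, HA correlates r with AUC-I as a whole, and the plan's main-effect-or-interaction rule is applied in a random-intercept model. At r = 0, 0.3, 0.5, 0.7 the joint AUC-I rates are 0, 6, 19, 47% with sleep effect 0.40, and 0, 14, 47, 83% with the pilot value 0.57. AUC-G at 0.57 gives 0, 0.4, 4.5, 14%. Draws 1-2 give 0.1% or less. These rates are higher because the reverse link acts on the whole summary and between-person variation also feeds the test.

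**The case against.** Several points on the other side stand.

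- Draw 3 is taken before the QST1 reading, so it does precede the measured outcome. What it does not precede is the sensitization being measured. Draw 4 precedes neither.
- The plan never names AUC-I as the 3.b mediator. A reader might infer that it does, and that pain-driven inflammation would therefore be reported as mediation. The text supports less: the AUCs are the only summaries tested in 3.a, both contain post-capsaicin blood, and the one used in 3.b is unstated. If it is AUC-G, the exposure is modest.
- The 3.a precondition does reduce the error. Quoting the link rates alone (13% to 100% above) would overstate the problem, since the plan requires both steps. The precondition is worded per marker, so a marker qualifying on AUC-G might then be tested on AUC-I, but the plan does not say this is intended.
- A reader might extend the point to all of 3.b. It does not carry over to opioid analgesia: those outcomes start at QST2, which draws 3 and 4 both precede.
- The plan's account of its cited mediation approach states no time-order rule. The argument here rests on the directional meaning of mediation, not on that source.
- Capsaicin reactivity is a deliberate and legitimate measure under Aim 3. It is better kept as an outcome than dropped. Resting draws do not remove marker-HA confounding either.

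**Conclusion.** The concern holds for the HA part of Hypothesis 3.b. As written, a significant marker-HA association built on AUC-G or AUC-I would be labelled mediation although the sampling times cannot distinguish inflammation acting on HA from HA, or the common stimulus, acting on the marker. The conflict over draw 4 stands on the documents alone.

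The size rests on assumptions that the documents do not supply. It is nil without a reverse effect. For slopes of 0.2 to 0.5 and draw correlations of 0.5 to 0.85, false AUC-I mediation runs from under 1% to about 30%. It is higher under more extreme correlation or the second set-up, and small if draw 1 is the baseline. AUC-G is affected at about 1-6% in the main set-up. A mediator from draws 1-2 holds the nominal 1%. These figures show that the rule can mislead; they do not predict how often it would.

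**What to change.** For the HA part of 3.b, name the mean of draws 1 and 2 as the primary mediator. These samples follow the sleep manipulation, precede capsaicin and are already planned. Test the sleep effect on that same mean as the condition for entering 3.b.

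Keep AUC-I as a 3.a outcome describing reactivity to capsaicin. Report AUC-I–HA and AUC-G–HA associations as concurrent, not as evidence of mediation.

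Reconcile draw 4 between the blood-draw schedule in 4.a and the pre-drug definition in 7.b, and leave any post-injection draw out of analyses that pool the drug arms. The opioid-analgesia part may keep draw 3, which precedes both the injection and the post-drug outcomes.

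The cost is SAP wording, with no new samples or visits. Two things are given up or left open: capsaicin-evoked reactivity can no longer be claimed as a mediator of HA, and confounding of the marker-HA relation remains and should be stated as a limitation.

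### AUC-I has two definitions that cannot both be followed: the usual formula scores the resting change from draw 1 to draw 2 as response, while the plan describes both draws as baseline

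*Combined protocol and SAP*

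**What the plan says.** Section 7.b, Hypothesis 3.a, opens: "We will first compute area-under-the-curve-ground (AUC-G) and -increase (AUC-I) values following standard formulas(134) for the inflammatory markers". No formula, ground value or integration window is printed. The same paragraph then says "AUC-I represents the level of increase in inflammation in response to heat capsaicin (blood draws 3-4), relative to the within-condition baseline levels" and gives draws 1 and 2 in brackets as that baseline. AUC-G is described as the total over draws 1 to 4, which the paragraph calls the pre-drug segment. Mixed models compare both AUCs between sleep conditions, and Hypothesis 3.b goes forward only for markers that 3.a links to sleep disruption.

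Section 4.a (Blood Draws & Handling Procedures) agrees on the role of the first two draws: they are about 60 minutes apart, "prior to the 35 minute heat capsaicin procedure, to provide a resting baseline". On draw 4 it does not agree with 7.b. It counts three draws before the injection and four after, and places every draw after the initial capsaicin procedure just before a rekindling. The Design and Heat-Capsaicin paragraphs put draw 3 at capsaicin removal, then QST1, the injection, a 40-minute rest and the first rekindling. On that schedule draw 4 follows the injection.

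**The concern.** The first sentence of Hypothesis 3.a names a method; a later one describes a result that the method, in its usual form, does not produce. An analyst who applies the usual formula treats draw 2 as response. An analyst who follows the description treats it as baseline. Draws 1 and 2 both precede capsaicin and lie about an hour apart, so the choice decides whether an hour of rest is scored as part of the response to capsaicin.

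AUC-I is one of the two summaries tested in 3.a, and 3.b takes its candidate mediators from those tests. If AUC-I carries resting change, the capsaicin response is measured with more noise than necessary. A difference between FA and US in how markers move after waking could also be reported as a difference in capsaicin-evoked inflammation. The draw 4 conflict adds to this: it decides whether AUC-I has one or two usable post-capsaicin samples, and whether the second is free of drug effect.

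**Working it through.** The documents give no figure for the weighting inside AUC-I, so there is none to reproduce. The Aim 3 power statement (N=80, alpha 0.01, effect of 0.56 or more) is not used to derive the weights.

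**Inputs from section 4.a:** draw 1 at 0 min; draw 2 at about 60 min; a 35-minute procedure (5 min heat, 30 min capsaicin); draw 3 at removal; injection after QST1; 40 min rest; then the first rekindling.

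**Assumptions, because not stated:** the usual AUC-I formula; no gap between draw 2 and the procedure (range 0 to 30 min); QST1 plus injection 20 min (range 0 to 60). Draw 3 is then at 60 + 35 = 95 min and draw 4 at 95 + 20 + 40 = 155 min.

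**Formula:** AUC-I = sum of (d_i + d_{i+1})/2 × (t_{i+1} − t_i), minus d1 × (t_last − t_1).

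**Draws 1 to 4:** 30(d1+d2) + 17.5(d2+d3) + 30(d3+d4) − 155·d1 = −125·d1 + 47.5·d2 + 47.5·d3 + 30·d4.
- A unit change between draws 1 and 2 that persists: 47.5 + 47.5 + 30 = 125.
- A unit change between draws 2 and 3 (across capsaicin) that persists: 47.5 + 30 = 77.5.
- Ratio: 125/77.5 = 1.61. Over the assumed timings it runs from 165/117.5 = 1.40 (no gap, QST1 60 min) to 135/72.5 = 1.86 (gap 30 min, QST1 0 min).
- The draw 1–2 change has 125/(125 + 77.5 + 30) = 54% of the total weight on successive changes (50% to 59% over the timings).

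**Draws 1 to 3 only:** −65·d1 + 47.5·d2 + 17.5·d3. The ratio is 65/17.5 = 3.7, or 95/32.5 = 2.9 with a 30-minute gap. The draw 1–2 change has 65/82.5 = 79% of the weight (75% with that gap).

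**Draw 4 before the injection, 5 to 30 min after draw 3:** the ratio is 70/22.5 = 3.1 down to 95/47.5 = 2.0.

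**Two invented records at 0/60/95/155 min**, scored by the usual formula and by the description (ground = mean of draws 1 and 2, area over the 60 min from draw 3 to draw 4):

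| d1, d2, d3, d4 | Usual formula | Description |
|---|---|---|
| 10, 11, 11, 11 (no capsaicin response) | 125 | 0.5 × 60 = 30 |
| 10, 10, 11, 11 (capsaicin response only) | 77.5 | 1 × 60 = 60 |

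The usual formula ranks the record with no capsaicin response higher; the described quantity ranks it lower. The description does not remove resting drift. It counts a lasting draw 1–2 change at half the weight of an equal capsaicin step.

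**Illustration only**, assuming independent noise of equal SD at each draw, 80 paired subjects and two-sided alpha 0.01. The comparator is the mean of the post-capsaicin values minus the mean of draws 1 and 2.
- Noise. Signal-to-noise for a capsaicin step, draws 1–4: 77.5/√(125² + 47.5² + 47.5² + 30²) = 0.534 against 1.000. For draws 1–3: 17.5/√(65² + 47.5² + 17.5²) = 0.212 against 1/√1.5 = 0.816, a ratio of 0.26. Where the comparator has 80% power (z = 2.576 + 0.842 = 3.418), AUC-I has z = 1.83 (power about 23%) or 0.89 (about 5%).
- Drift. With no capsaicin response and an FA–US difference in resting drift of 0.5 per-draw SD, AUC-I has z = 0.5 × 125 × √80/(√2 × 145.0) = 2.73 with draws 1–4 and 0.5 × 65 × √80/(√2 × 82.4) = 2.49 with draws 1–3. It is then significant in about 56% and 47% of trials, against about 16% and 10% for the comparator.

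**The case against.** The strongest reply is that the plan already states the intended quantity. Hypothesis 3.a names draws 1 and 2 as baseline and draws 3 and 4 as response, and the reference to standard formulas may mean only the area method, applied with that baseline. This stands in part. A reader might infer that draw 1 alone will certainly be the ground; the documents do not settle that. On the sponsor's reading, however, the reference to standard formulas is wrong for AUC-I and the same edit is needed.

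A reader might also infer that AUC-I would chiefly score pre-capsaicin change. With draws 1 to 4, the window that 7.b names, the share is about half, and draw 2 itself has only 47.5/125 = 38% of the weight on draws 2 to 4. The share is clearly above half only with draws 1 to 3. What AUC-I picks up in practice depends on how far markers move between draws 1 and 2, which the documents do not report.

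Nor do the documents support a claim of false sleep effects on inflammation in general. Drift common to FA and US cancels on average in the within-subject comparison. Drift that differs between them would itself be a sleep effect on a marker, within the broad wording of 3.a; the error would be attributing it to capsaicin. AUC-G is tested too and does not use a ground sample.

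Finally, the percentages are sensitive to their assumptions. If the capsaicin response varies between subjects with an SD equal to the draw SD, the draws 1–4 signal-to-noise ratio rises from 0.53 to 0.67, and at twice that SD to 0.82. The 0.5 SD drift difference has no source in the documents.

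**Conclusion.** The concern holds as an unresolved conflict of definition with a practical cost. The usual AUC-I formula and a baseline of draws 1 and 2 cannot both be followed. If the usual formula is used, a lasting resting change outweighs an equal change across capsaicin at every timing examined: about 1.4 to 1.9 times with draws 1 to 4 on the section 4.a schedule, and about 2.9 to 3.7 times with draws 1 to 3. Both ranges assume the first-sample formula and the stated spread of timings; 35 minutes from draw 2 to draw 3 is a lower bound, because the gap before the procedure is not given.

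The added noise needs no differential drift. Mislabelling needs drift that differs between FA and US, and no data on that are given. The power and false-signal percentages are illustrations and not forecasts for this trial. Which set of weights applies cannot be decided until 7.b and 4.a agree on draw 4.

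**What to change.** In section 7.b, Hypothesis 3.a, replace the reference to standard formulas for AUC-I with an explicit definition: ground equal to the mean of draws 1 and 2 within each admission; the draw 1–2 interval not counted as response; response taken only from named post-capsaicin, pre-injection draws, using actual sampling times. A simpler equivalent is the mean of those response values minus the mean of draws 1 and 2, compared between FA and US in the same mixed model. If only draw 3 qualifies there is no area to integrate, and this change score is the measure. AUC-G can stay as the summary of overall level, with its draws corrected if necessary.

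Reconcile the pre-drug segment in 7.b (draws 1 to 4) with the three pre-injection draws in 4.a and the order of injection, rest and rekindling in the Design and Heat-Capsaicin paragraphs. This decides whether draw 4 may enter either AUC, and it also affects the first part of 3.b, which pools the drug groups because its data are meant to be pre-drug.

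The cost is a sentence or two, with no new samples, visits or assays. The one downside is that AUC-I values will no longer be numerically comparable with publications that use the first-sample formula.
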